The objective of this study is to evaluate and compare the safety and effectiveness of High Purity Type-I Collagen-based Skin Substitute (HPTC) with Dehydrated Human Amnion/Chorion Membrane (dHACM) for treating diabetic foot ulcers (DFUs). This randomized, controlled clinical trial seeks to provide valuable insights into the best treatment strategy for enhancing healing outcomes and reducing the challenges posed by chronic DFUs.

Materials and Methods

Study will be carried out as a randomized, controlled open-label study to evaluate the safety and effectiveness of High Purity Type-I Collagen-based Skin Substitute (HPTC) compared to Dehydrated Human Amnion/Chorion Membrane (dHACM) for treating diabetic foot ulcers (DFUs). The trial will include patients with DFUs treated by wound care specialists at Adichunchanagiri Institute of Medical Sciences, B. G. Nagara, under the supervision of primary investigator [name] consent will be obtained from all participants prior to any study-related procedures, and each patient will sign an Institutional Ethics Committee/Investigational Review Board (IEC/IRB)-approved consent form. The investigator will comply with regulatory guidelines and Good Clinical Practice (GCP) in

obtaining and documenting informed consent. All study products will be produced, handled,

and stored in accordance with Good Manufacturing Practices (GMP). Strict patient confidentiality protocols will be maintained throughout the study.

Patient Screening and Eligibility

The study population will consist of patients seeking treatment for DFUs. Eligible patients will be those willing to participate and comply with scheduled visits on days 7, 10, 14, 17, 21, and 28. The study will include two phases: screening and treatment. The screening phase aimed to determine patient eligibility for the treatment phase. The inclusion and exclusion criteria are detailed in Table 1. During screening, a series of assessments will be conducted, including demographics, medical history, concomitant medications, vital signs, physical examination, leg ulcer history, clinical infection signs at the ulcer site.

Study Treatment:

The treatment phase of the study will commence with a series of evaluations to ensure patients remained eligible. Participants who will continue to meet the inclusion criteria after the screening phase will be randomly assigned to one of two groups:

- 1. Standard of Care (SOC) with High Purity Type-I Collagen-based Skin Substitute (HPTC).

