- 2. Standard of Care (SOC) with Dehydrated Human Amnion/Chorion Membrane (dHACM).

Neither the patients nor the clinicians will be blinded to group assignments. The randomization will follow a balanced schedule, using permuted blocks of 12. When a patient will be ready for randomization, the study site will contact a representative from the sponsor, who will open a sequentially numbered opaque envelope to disclose the group assignment, maintaining allocation concealment.

Throughout the 4-week treatment phase, patients will be reassessed on days 7, 10, 14, 17, 21, and 28. The SOC dressing applied in both groups consisted of a three-layer system:

- First layer: Non-adherent, porous paraffin gauze.
- Second layer: Absorbent gauze pads.
- Third layer: Soft roll and Crepe bandage.

Note:

- a. 2 sizes of HPTC used:
- i. 0.8 in x 1.6 in or 2 cm x 4 cm (8 sq cm)
- ii. 1.6 in x 1.6 in or 4 cm x 4 cm (16 sq cm)
 - b. 2 sizes of dHACM used:
- i. 5 cm x 5 cm (25 sq cm)
- ii. 8 cm x 6 cm (48 sq cm)

If the study ulcer was found to be 100% re-epithelialized during the visit, no further study procedures will be conducted at that time. The patient will then be scheduled for a follow-up visit after one week to confirm the healing.

If full healing was not achieved, an evaluation will be carried out to check for any signs of clinical infection. If an infection is confirmed, treatment with topical antimicrobials or oral antibiotics will be permitted, though the use of topical antibiotics will be prohibited. After this infection assessment, the ulcer would be cleaned, photographed, and debrided at the investigator's discretion to ensure a clean and granulating wound base with minimal adherent slough. The Standard of Care (SOC) will be then re-applied, and patients will be instructed to keep the bandage dry. Additionally, they will be advised to contact or return to the study site if the bandage became soiled or removed.

Study Completion:

Patients will complete the study 4 weeks after their initial treatment visit. However, if a patient's study ulcer healed before the 4-week period, they will be considered to have completed the study at the time of full healing.

Complete healing will be defined as 100% re-epithelialization of the ulcer with no drainage. Throughout the study, patients will retain the right to decline participation or withdraw at any time without prejudice.

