In the event of a patient's withdrawal, their last recorded wound measurement will be carried forward to determine the change in wound size and calculate their final outcome.

Study Outcomes:

Primary Endpoint:

• The primary outcome of the study will be the proportion of subjects who achieved improvement in wound healing, as observed on days 7, 10, 14, 17, 21, and 28. The wound closure of the target ulcer will be continuously monitored until the end of the 4-week period.

Secondary Endpoints:

- **Time to Achieve Complete Wound Closure:** Time taken for the target ulcer to achieve complete wound closure will be assessed on days 7, 10, 14, 17, 21, and 28.
- **Percentage Wound Area Reduction:** This will be measured weekly on days 7, 10, 14, 17, 21, and 28 using digital photography.
- **Mean Number of Repeated Applications of HPTC:** The average number of times the reapplication of High Purity Type-I Collagen-based Skin Substitute (HPTC) to achieve wound closure will be documented as part of the study process.

Exploratory Endpoint:

• The appearance, structural stability, and fragility of the newly formed skin will be documented at each visit. Any recurrence of the wound will also be monitored.

Subjects must be at least 18 years of age or older.	A subject known to have a life expectancy of less than 6 months.
Subjects must have a diagnosis of type 1 or 2 diabetes mellitus.	If the target ulcer is infected or if there is cellulitis in the surrounding skin.
At enrolment, subjects must have a target diabetic foot ulcer with a minimum surface area of 5.0 cm ² and a maximum surface area of 10.0 cm ² , measured post-debridement using a ruler.	Presence of osteomyelitis or exposed bone, probes to bone or joint capsule on investigator's exam, or radiographic evidence.
The target ulcer must have been present for a minimum of 4 weeks and a maximum of 52 weeks of standard care prior to the initial screening visit.	A subject that has an infection in the target ulcer that requires systemic antibiotic therapy.
The target ulcer must be located on the foot, with at least 50% of the ulcer below the malleolus.	A subject receiving immunosuppressants (including systemic corticosteroids at doses greater than 10 mg of prednisone per day or equivalent) or cytotoxic chemotherapy.
The target ulcer must be full thickness on the foot or ankle and must not probe to bone.	Topical application of steroids to the ulcer surface within one month of initial screening.

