Descriptive statistics will be used to summarize the data. Quantitative data will be presented as means or medians, while qualitative data will be expressed as frequencies and percentages. The study aims to assess the proportion of study participants achieving wound healing by the end of the fourth week. To measure the proportion of participants showing improvement in wound healing, observations will be conducted on days 7, 10, 14, 17, 21, and 28. The proportion of participants achieving wound healing would be compared between both the groups using Chisquare/ Fisher's exact test. Additionally, the average reduction in ulcer size from baseline to the end of the fourth week will be compared between groups, and the significance of the reduction will be analysed using the independent t test/Mann-Whitney U test.

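### One secondary endpoint is percentage wound area reduction, but its only analysis names no scale, leaves the test open and ignores baseline area

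*Combined protocol and SAP*

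**What the plan says.** - **Endpoint.** Secondary Endpoints lists three items. One is "Percentage Wound Area Reduction", with the note "This will be measured weekly on days 7, 10, 14, 17, 21, and 28 using digital photography".
- **Analysis.** The Statistical analysis section has one sentence on area: "the average reduction in ulcer size from baseline to the end of the fourth week will be compared between groups". No scale is given. The test is the "independent t test/Mann-Whitney U test", with no rule for choosing and no covariate.
- **Baseline area.** Table 1 requires a target ulcer of 5.0 to 10.0 cm² at enrolment, "measured post-debridement using a ruler". Under Study Treatment, the treatment phase "will commence with a series of evaluations to ensure patients remained eligible"; those evaluations are not itemised. At later visits where the ulcer has not healed, "the ulcer would be cleaned, photographed, and debrided", in that order. Nothing states which measurement is the denominator of the percentage.
- **Blinding.** Patients and clinicians know the assigned arm.
- **Not stated.** Sample size, alpha, power, SD and effect size.

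**The concern.** Percentage and cm² reduction rank patients differently when starting areas span a two-fold range. A 5 cm² ulcer that closes and a 10 cm² ulcer that half closes both lose 5 cm², yet they score 100% and 50%. A reader of the Statistical analysis section cannot tell which quantity will be tested, or by which test.

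Two things are at stake. First, power: an unadjusted test carries noise from starting size whenever the analysed scale depends on it, and the plan does not say how healing relates to size. Second, the choice of scale and test can be made after the data are seen, by people who may know the arms. That inflates the false-positive rate if the more favourable result is taken.

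**Working it through.** The plan has no figure to reproduce. Everything below rests on assumed inputs, apart from the 5 to 10 cm² range (Table 1) and balanced allocation (Study Treatment).

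**1. Definitions.** With A0 the baseline area and A28 the day 28 area:
- cm² reduction = A0 − A28
- percentage reduction = 100 × (A0 − A28)/A0
- ANCOVA: outcome = intercept + arm effect + slope × A0 + error

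**2. Why starting size matters on the cm² scale.** Let the healed fraction p be independent of A0, and A0 uniform on 5 to 10. Then E[A0] = 7.5, Var(A0) = 25/12 = 2.08 and E[A0²] = 56.25 + 2.08 = 58.33. Ignoring the cap at closure, Var(A0 × p) = 58.33 × Var(p) + (mean p)² × 2.08.
- Mean p 0.85, SD 0.20: 2.33 + 1.51, so 39% of the variance is only starting size.
- Mean p 0.425, SD 0.35: 7.15 + 0.38, so 5% is.

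The loss from an unadjusted cm² test can therefore be large or small.

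**3. Simulated power.** 6,000 trials per scenario, two-sided 0.05, A0 uniform on 5 to 10 cm².
- Pattern A, healing proportional to size: the healed fraction is normal and capped at 1.
- Pattern B, cm² loss independent of size: the loss is normal and capped at A0.

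Means and SDs are before capping. Entries are power in percent for cm² t test / percentage t test / percentage ANCOVA.

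| Scenario | 50 per arm | 36 per arm |
|---|---|---|
| A: 90 v 80%, SD 20 | 38.0 / 66.0 / 65.3 | 29.4 / 51.7 / 51.3 |
| A: 85 v 72%, SD 25 | 51.4 / 70.0 / 69.6 | 39.4 / 56.5 / 55.7 |
| A: 80 v 65%, SD 30 | 53.8 / 66.2 / 65.8 | 43.0 / 53.5 / 53.0 |
| A: 50 v 35%, SD 35 | 53.3 / 56.6 / 56.3 | 40.6 / 43.6 / 43.0 |
| B: 4.5 v 3.5 cm², SD 1.5 | 90.5 / 82.0 / 89.6 | 79.3 / 68.5 / 77.4 |
| B: 4.3 v 3.5 cm², SD 1.5 | 73.8 / 62.9 / 72.3 | 59.8 / 49.5 / 58.5 |
| B: 5.3 v 4.5 cm², SD 1.7 | 60.6 / 51.2 / 60.6 | 47.6 / 39.2 / 47.5 |
| B: 3.5 v 2.5 cm², SD 2 | 69.2 / 64.9 / 67.7 | 54.9 / 50.8 / 53.0 |
| B: 4.5 v 3.5 cm², SD 2 | 68.2 / 62.5 / 67.2 | 54.5 / 48.9 / 53.6 |

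- Pattern A, cm² t test against percentage ANCOVA: the smallest loss is 43.0 − 40.6 = 2.4 points and the largest 65.3 − 38.0 = 27.3. ANCOVA gains nothing over the percentage t test; it is 0.3 to 0.8 points lower.
- Pattern B, percentage t test against percentage ANCOVA: the smallest loss is 53.0 − 50.8 = 2.2 points and the largest 72.3 − 62.9 = 9.4.
- Six analyses were compared (t test, Mann-Whitney and ANCOVA on each scale). Percentage ANCOVA was within 1.9 points of the best in all 18 runs and cm² ANCOVA within 2.5. The protection comes from adjusting for area; percentage is preferred because it is the named endpoint.

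**4. False-positive rate.** Null simulations, 20,000 trials in each of 7 settings at both sample sizes:

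| Rule | Rate |
|---|---|
| One percentage ANCOVA | 4.8 to 5.3% |
| Smaller p of t and Mann-Whitney, percentage only | 5.5 to 6.2% |
| Smallest p over both scales and both tests | 7.4 to 9.8% |

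**5. Different assumptions.** A separate simulation used 60 per arm, percentage means of 90 v 75, SD 30, capped at 100, and 4,000 trials. With baseline unrelated to percentage reduction, power was 56.9% (cm² t test), 71.0% (cm² ANCOVA), 72.3% (percentage t test) and 71.4% (percentage ANCOVA). Under the null, over 30 and 60 per arm, the last two rules in step 4 gave 5.6 to 6.3% and 8.4 to 9.3%.

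**6. Measurement method.** If the baseline method overstates area by a constant factor k, percentage reduction becomes 100 − (100 − percentage)/k for everyone. That is a linear rescaling, so reported reductions shift but p-values do not. With k = 1.27 in 300 datasets, no p-value from any of the three tests changed by more than 1e-12.

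**The case against.** **The scale is implied.** Percentage reduction is the only area endpoint defined, so the analysis sentence may simply be shorthand for it. That is plausible, and it means the 7.4 to 9.8% rate requires an analyst to leave the named endpoint and try both scales. The sentence still does not say so, and the test stays open.

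**The slash may mean a distribution-based choice.** Choosing by Shapiro-Wilk in each arm, on percentage, gave 4.6 to 5.8% false positives in two null settings, against 4.8 to 5.6% for ANCOVA in the same trials. If that is the intended rule, inflation is negligible. The plan does not state it.

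**ANCOVA is a preference.** In part this stands. Naming percentage alone closes the 27-point gap, and the further gain exists only under pattern B, which the plan neither supports nor excludes. The simulated shapes are also narrow. With a fraction fully closed and lognormal residual areas, Mann-Whitney beat percentage ANCOVA by about 4 to 8 points in three of four settings (for example 43.9% v 36.5%); ANCOVA won by 11 to 17 in the fourth. This is why the rank test should be kept as a prespecified sensitivity analysis.

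**Stronger readings that the text does not support.**
- A reader might infer that the withdrawal rule, where "their last recorded wound measurement will be carried forward to determine the change in wound size", is a conflicting definition. It is not: either scale can be computed from the carried-forward measurement.
- A reader might infer that there is no baseline at all. Table 1 supplies one pre-treatment area; what is missing is a statement that it is the denominator.
- A reader might infer that the planned tests are invalid. Under randomisation, each is valid if fixed in advance.

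**Conclusion.** The concern holds as a gap in specification and efficiency, not as an error of validity. It affects one of three secondary endpoints and should be fixed.

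On assumed inputs, the possible loss against a percentage ANCOVA is 2 to 27 points of power for a cm² t test if healing is proportional to size, and 2 to 9 points for a percentage t test if cm² loss is independent of size. In the first case ANCOVA adds nothing to a percentage t test. If the named endpoint is respected, the open choice of test costs at most about one point of false-positive rate (5.5 to 6.2%). A rate near 10% would be the wrong summary, because it needs both scales to be tried.

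Confidence is medium. The textual gap is plain, but every magnitude depends on sample sizes, SDs, effects and outcome shapes that the plan does not give.

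**What to change.** In the Statistical analysis section:
1. Name percentage area reduction from baseline to day 28 as the analysed variable.
2. Analyse it by one prespecified ANCOVA with arm and baseline area, and report the between-arm difference with its 95% CI.
3. Keep Mann-Whitney as a prespecified sensitivity analysis, because the outcome is capped at 100%.
4. State which baseline measurement is the denominator, taken by the same method and at the same point relative to debridement as the follow-up measurements.

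The cost is a few lines of text and one model term; baseline area is already collected for eligibility. If photography is the chosen method, a baseline photograph must be specified. The statistical price is a linear model on a capped outcome, where a rank test can have more power under some distributions.
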